15.1 Patient selection and characteristics

15.1.1 Patient selection and characteristics in PHARMO

[figure not shown]

Figure 15.1 Flow chart of patient selection in PHARMO

NOTE: this flow chart will be repeated for each database. An additional level of ‘GP data available’ will be added for PHARMO

Table 15.1 General characteristics of new CPA/EE users in PHARMO per calendar year

| | 2011 starters N=7,876 n (%) | 2012 starters N=7,562 n (%) | 2014 starters N=1,401 n (%) | 2015 starters N=0,000 n (%) | 2016 starters N=0,000 n (%) | 2017 starters N=0,000 n (%) |
|---|--|--|--|--|--|--|
| Age (years) | | | | | | |
| <15 | 278 (4) | 262 (3) | 13 (1) | | | |
| 15-<25 | 3,986 (51) | 3,733 (49) | 482 (34) | | | |
| 25-<35 | 2,385 (30) | 2,365 (31) | 584 (42) | | | |
| 35-<45 | 1,001 (13) | 968 (13) | 242 (17) | | | |
| 45-<55 | 211 (3) | 229 (3) | 73 (5) | | | |
| ≥55 | 15 (<0.5) | 5 (<0.5) | 7 (<0.5) | | | |
| mean ± SD | 25 ± 9 | 25 ± 9 | 29 ± 9 | | | |
| median (IQR) | 23 (18-31) | 24 (18-31) | 27 (23-34) | | | |
| Database history before index date (years) | | | | | | |
| 1-<2 | 420 (5) | 418 (6) | 91 (6) | | | |
| 2-4 | 966 (12) | 648 (9) | 140 (10) | | | |
| >4 | 6,490(82) | 6,496 (86) | 1,170 (84) | | | |
| mean ± SD | 8 ± 4 | 9 ± 4 | 9 ± 5 | | | |
| median (IQR) | 7 (5-12) | 8 (6-13) | 9 (6-11) | | | |
| Follow-up after index date (months)* | | | | | | |
| <6 | 3,877 (49) | 3,573 (47) | 641 (46) | | | |
| 6-12 | 3,999 (51) | 3,989 (53) | 760 (54) | | | |
| mean ± SD | 6 ± 3 | 6 ± 3 | 6 ± 3 | | | |
| median (IQR) | 6 (3-9) | 6 (3-9) | 6 (3-9) | | | |

* by definition, the follow-up will not be longer than 12 months (see section 9.2).

15.1.2 Patient selection and characteristics in THIN

[figure not shown]

Figure 15.2 Flow chart of patient selection in THIN

Table 15.2 General characteristics of new CPA/EE users in THIN per calendar year

| | 2011 starters N=2,760 n (%) | 2012 starters N=2,923 n (%) | 2014 starters N=2,341 n (%) | 2015 starters N=0,000 n (%) | 2016 starters N=0,000 n (%) | 2017 starters N=0,000 n (%) |
|---|--|--|--|--|--|--|
| Age (years) | | | | | | |
| <15 | 154 (6) | 175 (6) | 136 (6) | | | |
| 15-<25 | 1,520 (55) | 1,617 (55) | 1,310 (56) | | | |
| 25-<35 | 866 (31) | 907 (31) | 709 (30) | | | |
| 35-<45 | 208 (8) | 209 (7) | 176 (8) | | | |
| 45-<55 | 11 (<0.5) | 14 (<0.5) | 10 (<0.5) | | | |
| ≥55 | 1 (<0.5) | 1 (<0.5) | 0 (0) | | | |
| mean ± SD | 23 ± 7 | 23 ± 7 | 23 ± 7 | | | |
| median (IQR) | 22 (17-28) | 22 (17-28) | 22 (17-28) | | | |
| Database history before index date (years) | | | | | | |
| 1-<2 | 171 (6) | 219 (7) | 163 (7) | | | |
| 2-4 | 248 (9) | 223 (8) | 179 (8) | | | |
| >4 | 2,341 (84) | 2,481 (85) | 1,999 (85) | | | |
| mean ± SD | 11 ± 6 | 12 ± 6 | 12 ± 7 | | | |
| median (IQR) | 12 (6-16) | 12 (6-16) | 13 (7-17) | | | |
| Follow-up after index date (months)* | | | | | | |
| <6 | 1,316 (48) | 1,351 (46) | 1,108 (47) | | | |
| 6-12 | 1,444 (52) | 1,572 (54) | 1,233 (53) | | | |
| mean ± SD | 6 ± 4 | 6 ± 4 | 6 ± 4 | | | |
| median (IQR) | 6 (3-9) | 6 (3-9) | 6 (3-9) | | | |

* by definition, the follow-up will not be longer than 12 months (see section 9.2).

15.1.3 Patient selection and characteristics in HSD

[figure not shown]

Figure 15.3 Flow chart of patient selection in HSD

Table 15.3 General characteristics of new CPA/EE users in HSD per calendar year

| | 2011 starters N=495 n (%) | 2012 starters N=446 n (%) | 2014 starters N=261 n (%) | 2015 starters N=0,000 n (%) | 2016 starters N=0,000 n (%) | 2017 starters N=0,000 n (%) |
|---|--|--|--|--|--|--|
| Age (years) | | | | | | |
| <15 | 5 (1) | 0 (0) | 1 (<0.5) | | | |
| 15-<25 | 207 (42) | 212 (48) | 105 (40) | | | |
| 25-<35 | 146 (29) | 120 (27) | 83 (32) | | | |
| 35-<45 | 93 (19) | 71 (16) | 47 (18) | | | |
| 45-<55 | 36 (7) | 33 (7) | 19 (7) | | | |
| ≥55 | 8 (2) | 10 (2) | 6 (2) | | | |
| mean ± SD | 29 ± 10 | 29 ± 10 | 29 ± 11 | | | |
| median (IQR) | 26 (21-36) | 25 (21-35) | 26 (21-36) | | | |
| Database history before index date (years) | | | | | | |
| 1-<2 | 18 (4) | 14 (3) | 11 (4) | | | |
| 2-4 | 41 (8) | 36 (8) | 27 (10) | | | |
| >4 | 436 (88) | 396 (89) | 223 (85) | | | |
| mean ± SD | 11 ± 7 | 11 ± 6 | 12 ± 7 | | | |
| median (IQR) | 11 (6-15) | 11 (7-15) | 12 (7-16) | | | |
| Follow-up after index date (months)* | | | | | | |
| <6 | 232 (47) | 224 (50) | 118 (45) | | | |
| 6-12 | 263 (53) | 222 (50) | 143 (55) | | | |
| mean ± SD | 6 ± 4 | 6 ± 4 | 6 ± 4 | | | |
| median (IQR) | 6 (3-9) | 6 (3-9) | 7 (3-10) | | | |

* by definition, the follow-up will not be longer than 12 months (see section 9.2).

15.2 Concomitant use of hormonal contraceptives

15.2.1 Concomitant use of hormonal contraceptives in PHARMO

Table 15.4 Concomitant use of other HC among new CPA/EE users in PHARMO per calendar year

| | 2011 starters N=0,000 n (%) | 2012 starters N=0,000 n (%) | 2014 starters N=0,000 (%) | 2015 starters N=0,000 n (%) | 2016 starters N=0,000 n (%) | 2017 starters N=0,000 n (%) |
|---|--------------------------------------|--------------------------------------|------------------------------------|--------------------------------------|--------------------------------------|--------------------------------------|
| Number of CPA/EE episodes during follow-up 1 2 ≥3 mean ± SD median (IQR) Summed duration of CPA/EE use (months) ¹⁾ 0-3 4-6 7-12 mean ± SD median (IQR) | | | | | | |
| Concomitant use Concomitant and potential concomitant use ²⁾ Potential concomitant use Non-concomitant use No use of other HC Duration of concomitant use of other HC ≤28 days >28 - 84 days >84 days mean ± SD median (IQR) Duration of potential concomitant use of other HC (days) ≤28 days >28 - 84 days >84 days mean ± SD median (IQR) | | | | | | |

1) by definition, the follow-up and thus summed duration of use will not be longer than 12 months (see section 9.2).

2) A user may be concomitant and potential concomitant user at different times during CPA/EE use.

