Table 5.1 Amendments and updates to the Study Protocol

| Number | Date | Section of Study Protocol | Amendment or update | Reason |
|---------------|---------------|---|---|--|
| 1 | 30 March 2015 | 9.2 Setting | A prescription of CPA/EE in the year prior to index date was an exclusion criterion. In PHARMO, users were excluded as prevalent also when the prescription was more than one year prior to the index date but expired less than one year before the index date. | Exclusion of these women was more accurate. |
| 2 | 30 March 2015 | 9.2 Setting | In the Study Protocol an analysis of 2011/2012 was planned as well as an analysis of 2011 and 2012 separately. In the study report, only the calendar year analysis is presented. | The difference in recruitment periods between the analyses was confusing and the results in the analyses were similar. As the comparison of the 2014 analysis will be with the calendar years cohorts, it was decided to only present these. |
| 3 | 29 May 2015 | 9.2 Setting | PHARMO and HSD users who were new users in 2011 as well as in 2012, i.e. were using CPA/EE for a short time in 2011 and re-started after more than 365 days in 2012, were included in both populations. In THIN the 365-day period was applied before the date of study period entry, i.e. before Jan 1, 2011. By definition no users could re-enter in 2012. | At CEIFE standard procedure is to apply the medication-free period to the time before entry date rather than the index date. In practice this leads to only very small differences in numbers of users selected. |
| 4 | 29 May 2015 | 9.3 Variables | The index date was included in the assessment of diagnoses of acne and other hyperandrogenic conditions. | Extending the time window up to the index date also included the diagnoses recorded on the date of CPA/EE prescription, i.e. the likely indication of use. |
| 5 | 19 June 2015 | 9.3.2 Definition of switching and (potential) concomitant use of CPA/EE and hormonal contraceptives | In THIN, HC episodes were only created after the index date, not before. Overlap between other HC and CPA/EE before index date was assessed examining overlap between HC prescriptions and the first CPA/EE episode. | Different interpretation of the Study Protocol and different local standard programs. |

Table 5.1 Amendments and updates to the Study Protocol

| Number | Date | Section of Study Protocol | Amendment or update | Reason |
|--------|------------|---------------------------------|---|---|

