9.2 Setting

The study population will include all individuals registered in the databases receiving CPA/EE (ATC G03HB01) and Gemscript codes (85864998, 86466998, 86925998, 87351998, 90826979, 91068998, 91069998, 94832990, 94913992, 94920998, 95396990, 96577998 and 97520998) between January 1, 2011 and December 31, 2012 (study period for the first run) or January 1, 2014 and December 31, 2014 (study period for the second run). The year 2013 is not included in the identification period, as this is the year in which changes in policies and recommendations for CPA/EE usage have been implemented. The date of receiving the first prescription of CPA/EE in the study period will be defined as the index date.

The annual study periods for the 2017 extension will be between January 1 and December 31 of 2015, 2016 and 2017, respectively.

Exclusion criteria are:

- Men
- <365 days recorded history in the database prior to index date
- Use of CPA/EE in the year prior to the index date, defined by
 - a prescription of CPA/EE in the year prior to index date, or
 - a prescription of CPA/EE in the year prior to entry date (start of the study period or database entry, whichever occurred first) (THIN only, see Table 5.1 deviation #3) or
 - expiration of a prescription of CPA/EE in the year prior to index date (PHARMO only, see Table 5.1 deviation #1)

Patients will be followed from index date to transfer out of the database (end of follow-up available/censoring), end of study period, whichever occurs first. The first run will include an overall analysis (2011-2012) and an analysis by calendar year (2011 and 2012), for which separate recruitments will be performed (i.e. summing patients from the analysis by calendar year 2011 and 2012 may give a higher number than for the overall analysis). In the analysis by calendar year the end of the study period will be defined as December 31 of the year of index date (December 31, 2011, December 31, 2012).

For the 2017 study extension an analysis by calendar years will be performed..

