Prior treatment of acne, according to European treatment guidelines², will be assessed in the year prior to the index date (index date – 365 days, excluding index date; for included product names and ATC codes see Table 16.3 and Table 16.4 in Annex 2). Acne treatments will be classified as topicals, systemic preparations and hormonal agents and assessed separately for patients with and without an acne diagnoses in the year prior to index date. Because many of the drugs in the tables are not specific for acne, a pragmatic approach will be taken to select actual acne treatment in the study population: 1) select drugs by ATC or Gemscript code; 2) define dose and route of administration; 3) check with local guidelines for the approved indication of use and only include drugs that are approved for acne (alternative indications may exist). This check with the local guidelines is efficient because only the drugs that are actually used in the study population have to be checked once this data is available. Acne treatments will be further classified to whether it is only approved for acne, or also approved for other indications to allow sensitivity analysis.

Prior diagnoses of hyperandrogenic conditions or medical conditions where EE/progestin combinations are prescribed for frequently will be assessed in the year prior to index date (index date – 365 days, excluding index date; for included codes, see Table 16.5 and Table 16.6):

- Acne
- Alopecia
- Contraceptive management
- Hirsutism
- Menstrual problems
- Oligomenorrhoea/amenorrhoea
- Polycystic ovary syndrome (PCOS)
- Seborrhoea

For the 2017 study extension the following will be assessed:

Demographic characteristics:

- Age at index date (in years, categorized, mean (\pm SD), median (IQR))
- History available prior to the index date (in years, categorized, mean (\pm SD), median (IQR))
- Follow-up available after the index date (in months, categorized, mean (\pm SD), median (IQR))

Concomitant use of hormonal contraceptives:

- Number of CPA/EE treatment episodes (categorized, mean (\pm SD), median (IQR))
- Summed duration of CPA/EE use (in months, categorized, mean (\pm SD), median (IQR))
- Concomitant use of hormonal contraceptives (concomitant, potential concomitant, non-concomitant or no use of hormonal contraceptives)
- Duration of concomitant use of CPA/EE and hormonal contraceptives (≤ 28 days concomitant use, $>28 - 84$ days concomitant use or >84 days concomitant use, mean (\pm SD), median (IQR))

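### Summed CPA/EE duration in Tables 15.4-15.6 is cut at each woman's time left in the index year and summarised without allowance for it, so it is biased downward and cannot be read as duration of use

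*Protocol*

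**What the plan says.** Protocol section 9.2 starts the clock on any day of the year: "The date of receiving the first prescription of CPA/EE in the study period will be defined as the index date". It stops it on a fixed date: "In the analysis by calendar year the end of the study period will be defined as December 31 of the year of index date". For the extension, "The annual study periods for the 2017 extension will be between January 1 and December 31 of 2015, 2016 and 2017, respectively", and section 9.2 specifies an analysis by calendar year. Table 5.1 (item 2) records the same choice for the earlier cohorts: "In the study report, only the calendar year analysis is presented".

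Section 9.3 lists, among the extension variables, "Summed duration of CPA/EE use (in months, categorized, mean" with SD, and median with IQR. Section 9.7 prescribes means and medians for continuous data. Tables 15.4-15.6 use classes of 0-3, 4-6 and 7-12 months and carry the footnote that "the follow-up and thus summed duration of use will not be longer than 12 months".

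None of these places gives a censoring method, a common observation window or a count of women still using on 31 December. Section 9.9 does not list the cut among the limitations.

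**The concern.** A woman who starts in October can contribute at most three months, however long she goes on using CPA/EE. The footnote names a 12-month maximum, but only a woman who starts at the very beginning of January can come near it. A plain mean or median of such values mixes women who stopped with women who were still using when observation ended.

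Duration of use is a stated variable of both the main study and the extension. A reader who takes the mean, the median or the share in the 7-12 month class as a description of how long women use CPA/EE would conclude that use is shorter than it is.

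**Working it through.** **Inputs.** Index date and 31 December cut: section 9.2. Follow-up counts and summaries: Tables 15.1-15.3. True duration of CPA/EE use: not given anywhere, so assumed and varied below.

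**1. Reproduce the protocol's follow-up.** If starts are spread evenly over the year, follow-up F is uniform on 0 to 12 months: mean 12/2 = 6, SD 12/√12 = 3.46, median 6, IQR 3-9, 50% under 6 months. The filled tables show:
- mean 6 in all nine cohorts, SD 3 (PHARMO) or 4 (THIN, HSD);
- median 6 (3-9) in eight cohorts and 7 (3-10) in HSD 2014;
- under 6 months in 2011, 2012 and 2014: PHARMO 49.2%, 47.2%, 45.8%; THIN 47.7%, 46.2%, 47.3%; HSD 46.9%, 50.2%, 45.2%.

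Pooled: (8,091 + 3,775 + 574)/(16,839 + 8,024 + 1,202) = 12,440/26,065 = 47.7%. Follow-up is, in effect, the time left in the year.

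**2. The ceiling.** The lower quartile of follow-up is 3 months in all nine cohorts, so about a quarter of women cannot exceed about 3 months of summed use. About 48% cannot reach 7-12. If every woman used CPA/EE for a full 12 months, the table would show a mean and median of 6 and about 25%, 25% and 50% in the three classes.

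**3. Share above 6 months.** For uninterrupted use T that does not depend on start date, P(observed > 6) = P(T > 6) × P(F > 6). With the pooled figure, P(F > 6) is about 1 − 0.477 = 0.52. The share above 6 months is thus roughly halved, whatever the distribution of T.

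**4. Mean, under assumed exponential use.** With true median M, let m = M/ln 2.
- Full 12-month window: mean = m(1 − e^(−12/m)).
- As planned, F uniform: mean = ∫₀¹² e^(−t/m)(1 − t/12) dt = m − (m²/12)(1 − e^(−12/m)).
- Still using at the cut: (full-window mean)/12.

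Example, M = 6: m = 8.656 and e^(−12/m) = 0.25. The full-window mean is 8.656 × 0.75 = 6.49. The planned mean is 8.656 − (74.93/12) × 0.75 = 3.97. The shortfall is (6.49 − 3.97)/6.49 = 39%.

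| True median (months) | Mean as planned | Mean, full 12 months | Shortfall | Still using at the cut |
|---|---|---|---|---|
| 2 | 2.20 | 2.84 | 22% | 24% |
| 3 | 2.87 | 4.06 | 29% | 34% |
| 6 | 3.97 | 6.49 | 39% | 54% |
| 9 | 4.51 | 7.83 | 42% | 65% |
| 12 | 4.82 | 8.66 | 44% | 72% |
| 24 | 5.36 | 10.14 | 47% | 84.5% |

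A simulation with 1,000,000 draws agrees to within 0.01 month on the means.

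**5. Comparison between years.** Follow-up under 6 months varies only from 45% to 50% across cohorts, so an unchanged pattern of use would give nearly unchanged figures. A real difference keeps its direction but shrinks. True medians of 6 and 12 months differ by 8.66 − 6.49 = 2.17 months over a full window, and by 4.82 − 3.97 = 0.85 month as planned.

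**The case against.** The quantity is defined and partly disclosed. Section 9.3 measures duration from index date to end of follow-up, section 9.2 itself calls transfer out of the database censoring, the footnote points back to section 9.2, and Tables 15.1-15.3 print the follow-up distribution for the same cohorts. Nowhere does the protocol say that 31 December is the end of use. This stands, and it makes the existing rows correct as observed use within the year. It does not remove the problem: the footnote gives a common 12-month maximum rather than individual limits averaging 6, and section 9.9 is silent.

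Table 5.1 (item 6) also records the regulator's request for the same methodology and presentation as before, and duration is an extension variable rather than one of the objectives in section 8.2. Both points stand, so the rows should stay and anything new should be added beside them.

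Three stronger readings are tempting and are not supported.
- *The table mainly reports time left in the year.* That depends on how long women use CPA/EE, which the documents do not say. In the simulation, time left explains 10% to 18% of the variation in observed duration at true medians of 2 to 3 months, and about half only from about 9 months (47% at 9, 56% at 12).
- *The bias is of known size.* Only its direction and the ceilings follow from the protocol; the percentages need the exponential assumption.
- *The share with concomitant use is biased to a similar degree.* Contraceptive episodes are built from 365 days before index, so overlap already present when CPA/EE starts is captured however late in the year that is. The same cut applies to overlap arising later and to the duration of overlap, but the documents do not allow its effect to be sized.

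Table 14.4 has the same cut but different classes, and belongs to the analysis whose final report was planned for March 2016. The point is therefore confined to Tables 15.4-15.6.

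**Conclusion.** The point holds for the level of the reported duration. Each value is truncated at the time left in the index year, with a median of about 6 months and 47.7% of women under 6 months, and is summarised as if complete. The bias is downward. Its size is about 22% to 47% of the full 12-month mean, assuming starts spread evenly over the year, exponential use with true median 2 to 24 months, and duration independent of start date. The even spread is supported by the protocol's own follow-up tables; the other two are assumptions. The comparison between calendar years is much less affected: the cut creates no false trend, though it compresses real differences. This is a correction worth making because it is cheap, not a flaw that undermines the trend objective.

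**What to change.** 1. Keep the duration rows in Tables 15.4-15.6 for continuity, and label them 'observed within the index calendar year'.
2. State the truncation in section 9.9, with the median follow-up of about 6 months.
3. Add the percent still using CPA/EE at the cut.
4. Add a Kaplan-Meier summary of time to end of the first CPA/EE episode: percent continuing at 3 and 6 months, and the median if reached, with 31 December and transfer out as censoring. Restrict it to the first episode, because censoring is informative for duration summed over several episodes. Note that, since section 9.3.1 allows no gap between prescriptions, this measures time to first interruption, not summed use.
5. Optionally, report duration over a fixed window from index. Footnote that 12-month windows for 2012 starters run into 2013, the year section 9.2 leaves out of the identification period because policy changed. With 2017 data arriving in mid-2018, 2017 supports only a 6-month window in January-June starters.

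The cost is a few extra rows and one standard survival summary per database. If 2011, 2012 and 2014 are to be shown on the same basis, those cohorts must be re-run at the three centres.

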15.2.1 Concomitant use of hormonal contraceptives in THIN

Table 15.5 Concomitant use of other HC among new CPA/EE users in PHARMO per calendar year

| | 2011 starters N=0,000 n (%) | 2012 starters N=0,000 n (%) | 2014 starters N=0,000 (%) | 2015 starters N=0,000 n (%) | 2016 starters N=0,000 n (%) | 2017 starters N=0,000 n (%) |
|--|--------------------------------------|--------------------------------------|------------------------------------|--------------------------------------|--------------------------------------|--------------------------------------|
| Number of CPA/EE episodes during follow-up 1 2 ≥3 mean ± SD median (IQR) | | | | | | |
| Summed duration of CPA/EE use (months) ¹⁾ 0-3 4-6 7-12 mean ± SD median (IQR) | | | | | | |
| Concomitant use Concomitant and potential concomitant use ²⁾ Potential concomitant use Non-concomitant use No use of other HC | | | | | | |
| Duration of concomitant use of other HC ≤28 days >28 - 84 days >84 days mean ± SD median (IQR) | | | | | | |
| Duration of potential concomitant use of other HC (days) ≤28 days >28 - 84 days >84 days mean ± SD median (IQR) | | | | | | |

1) by definition, the follow-up and thus summed duration of use will not be longer than 12 months (see section 9.2).

2) A user may be concomitant and potential concomitant user at different times during CPA/EE use.

15.2.2 Concomitant use of hormonal contraceptives in HSD

Table 15.6 Concomitant use of other HC among new CPA/EE users in PHARMO per calendar year

| | 2011 starters N=0,000 n (%) | 2012 starters N=0,000 n (%) | 2014 starters N=0,000 (%) | 2015 starters N=0,000 n (%) | 2016 starters N=0,000 n (%) | 2017 starters N=0,000 n (%) |
|--|--------------------------------------|--------------------------------------|------------------------------------|--------------------------------------|--------------------------------------|--------------------------------------|
| Number of CPA/EE episodes during follow-up 1 2 ≥3 mean ± SD median (IQR) | | | | | | |
| Summed duration of CPA/EE use (months) ¹⁾ 0-3 4-6 7-12 mean ± SD median (IQR) | | | | | | |
| Concomitant use Concomitant and potential concomitant use ²⁾ Potential concomitant use Non-concomitant use No use of other HC | | | | | | |
| Duration of concomitant use of other HC ≤28 days >28 - 84 days >84 days mean ± SD median (IQR) | | | | | | |
| Duration of potential concomitant use of other HC (days) ≤28 days >28 - 84 days >84 days mean ± SD median (IQR) | | | | | | |

1) by definition, the follow-up and thus summed duration of use will not be longer than 12 months (see section 9.2).

2) A user may be concomitant and potential concomitant user at different times during CPA/EE use.

16. Annex 3. Additional information: code lists

Table 16.1 ATC codes to identify hormonal contraceptives in PHARMO and HSD

| Substance | ATC code |
|--|----------|
| Contraceptives for topical use | |
| plastic IUD with progestogen | G02BA03 |
| vaginal ring with progestogen and estrogen | G02BB01 |
| Hormonal contraceptives for systemic use | |
| Progestogens and oestrogens, fixed combinations | |
| Etynodiol and ethinylestradiol | G03AA01 |
| Quingestanol and ethinylestradiol | G03AA02 |
| Lynestrenol and ethinylestradiol | G03AA03 |
| Megestrol and ethinylestradiol | G03AA04 |
| Norethisterone and ethinylestradiol | G03AA05 |
| Norgestrel and ethinylestradiol | G03AA06 |
| Levonorgestrel and ethinylestradiol | G03AA07 |
| Medroxyprogesterone and ethinylestradiol | G03AA08 |
| Desogestrel and ethinylestradiol | G03AA09 |
| Gestodene and ethinylestradiol | G03AA10 |
| Norgestimate and ethinylestradiol | G03AA11 |
| Drospirenone and ethinylestradiol | G03AA12 |
| Norelgestromin and ethinylestradiol | G03AA13 |
| Nomegestrol and estradiol | G03AA14 |
| Chlormadinone and ethinylestradiol | G03AA15 |
| Dienogest and ethinylestradiol | G03AA16 |
| Progestogens and oestrogens, sequential preparations | |
| Megestrol and oestrogen | G03AB01 |
| Lynestrenol and oestrogen | G03AB02 |
| Levonorgestrel and oestrogen | G03AB03 |
| Norethisterone and oestrogen | G03AB04 |
| Desogestrel and oestrogen | G03AB05 |
| Gestodene and oestrogen | G03AB06 |
| Chlormadinone and oestrogen | G03AB07 |
| Dienogest and oestrogen | G03AB08 |
| Progestogens | |
| Norethisterone | G03AC01 |
| Lynestrenol | G03AC02 |
| Levonorgestrel | G03AC03 |
| Quingestanol | G03AC04 |
| Megestrol | G03AC05 |
| Medroxyprogesterone | G03AC06 |

| | |
|----------------|---------|
| Norgestrienone | G03AC07 |
| Etonogestrel | G03AC08 |
| Desogestrel | G03AC09 |

NOTE: emergency contraceptives (ATC G03AD) are not included.

Table 16.2 Gemscript codes to identify hormonal contraceptives in THIN

| Gemscript | Descriptor |
|---|---|
| first & later first generation | |
| 90566998 | Ethinylestradiol with norethisterone - biphasic 7 x 35mcg+500mcg; 14 x 35mcg+1mg Tablet |
| 90703997 | Ethinylestradiol with norethisterone - triphasic 7 x 35+500mcg; 7 x 35+750mcg; 7 x 35mcg+1mg Tablet |
| 90703998 | Ethinylestradiol with norethisterone - triphasic 7x35+500mcg; 9x35mcg+1mg; 5x35+500mcg Tablet |
| 92682998 | Mestranol with norethisterone Tablet |
| 93280992 | ETHINYLLOESTRADIOL 50MCG/ETHYNODIOL 1MG MCG TAB |
| 93334992 | ETHINYLLOESTRADIOL 30MCG/ETHYNODIOL 2MG MCG TAB |
| 94158996 | Ethinylestradiol 30microgram / Norethisterone acetate 1.5mg tablets |
| 94158997 | Ethinylestradiol 20microgram / Norethisterone acetate 1mg tablets |
| 94408992 | ANOVLAR 21 TAB |
| 94994992 | ETHINYLLOESTRAD. 50MCG/NORETHISTERONE 3MG MCG TAB |
| 94995992 | ETHINYLLOESTRADIOL/NORETHISTERONE 35 MCG TAB |
| 95289992 | MINOVLAR TAB |
| 95338992 | NORLESTRIN TAB |
| 95885998 | Mestranol 50microgram / Norethisterone 1mg tablets |
| 97470998 | Ethinylestradiol with norethisterone and placebo 50mcg + 1mg Tablet |
| 97472998 | Ethinylestradiol with norethisterone acetate 50mcg + 1mg Tablet |
| 97474998 | Ethinylestradiol with norethisterone acetate 50micrograms + 3mg Tablet |
| 97476998 | Ethinylestradiol with norethisterone acetate 50micrograms + 3mg Tablet |
| 97563998 | Generic Synphase tablets |
| 98085997 | Ethinylestradiol 35microgram / Norethisterone 1mg tablets |
| 98085998 | Ethinylestradiol 35microgram / Norethisterone 500microgram tablets |
| 98181997 | Ethinylestradiol with norethisterone - triphasic and placebo 7 x 35+500mcg; 7 x 35+750mcg; 7 x 35mcg+1mg Tablet |
| 98181998 | Generic Trinovum tablets |
| 98183998 | ETHINYL+NORETH 35/500mcg tabs |
| 98185998 | MESTRANOL+NORETHIST 50mcg/1mg |
| 98187998 | ETHINYL+NORETH 35mcg/1mg tabs |
| 98189998 | Generic Binovum tablets |
| 98191998 | MESTRANOL+NORETHIST 50mcg/1mg |
| 98193998 | ETHINYL+NORETH 35/500mcg tabs |
| 98195998 | ETHINYL+NORETH 35mcg/1mg tabs |
| 98207998 | ETHINY+NORETH 30mcg/1.5mg tabs |
| 98209998 | ETHINYL+NORETH 20mcg/1mg tabs |
| Second generation | |
| 89080998 | Generic Microgynon 30 ED tablets |
| 89213998 | Ethinylestradiol with levonorgestrel and placebo 30micrograms + 150micrograms Tablet |
| 89341998 | Ethinylestradiol with levonorgestrel 30micrograms + 50micrograms Tablet |
| 90641998 | Ethinylestradiol with levonorgestrel - triphasic with placebo 6x30+50mcg; 5x40+75mcg; |

| | |
|-----------------------|---|
| | 10x30+125mcg Tablet |
| 90644998 | Ethinylestradiol with levonorgestrel - triphasic 6x30+50mcg; 5x40+75mcg; 10x30+125mcg Tablet |
| 90647998 | Levonorgestrel 250microgram / Ethinylestradiol 50microgram tablets |
| 90650998 | Levonorgestrel 250microgram / Ethinylestradiol 30microgram tablets |
| 90654998 | Ethinylestradiol 30microgram / Levonorgestrel 150microgram tablets |
| 90972998 | Ethinylestradiol 35microgram / Norgestimate 250microgram tablets |
| 94997992 | ETHINYLLOESTRADIOL/LEVONORGESTREL 30 MCG TAB |
| 95002992 | ETHINYLLOEST+LEVONOR 50/250mcg |
| 97462998 | Generic Logynon ED tablets |
| 97464998 | ETHINYL+LEVONOR 30/150mcg tabs |
| 97466998 | ETHINYL+LEVONOR 30/250mcg tab |
| 98197998 | Generic Logynon tablets |
| 98199998 | ETHINYL+LEVONOR 30/150mcg tabs |
| 98201998 | ETHINYL+LEVONOR 30/250mcg tab |
| 98203998 | ETHINYLLOEST+LEVONOR 50/250mcg |
| 98205998 | Generic Logynon tablets |
| 99036998 | ETHINYL+NORGES 35/250mcg tabs |
| 99047998 | Norgestimate with ethinylestradiol 250micrograms + 35micrograms Tablet |
| 3rd generation | |
| 84491998 | ETHINYL+GESTODEN 20/75mcg tabs |
| 84492998 | ETHINYL+GESTODEN 30/75mcg tabs |
| 90747998 | Ethinylestradiol 30microgram / Desogestrel 150microgram tablets |
| 90750998 | Ethinylestradiol 20microgram / Desogestrel 150microgram tablets |
| 90757998 | Ethinylestradiol with gestodene - triphasic 6 x 30+50mcg; 5 x 40+70mcg; 10 x 30+100mcg Tablet |
| 90760998 | Ethinylestradiol with gestodene and placebo 30micrograms + 75micrograms Tablet |
| 90969997 | Ethinylestradiol 20microgram / Gestodene 75microgram tablets |
| 90969998 | Ethinylestradiol 30microgram / Gestodene 75microgram tablets |
| 92485998 | ETHINYL+GESTODEN 20/75mcg tabs |
| 93263998 | ETHINYL+GEST+PLAC 30/75mcg tabs |
| 94398997 | Gestodene with ethinylestradiol 75microgramwith20microgram Tablet |
| 94398998 | Gestodene with ethinylestradiol 75microgramwith30microgram Tablet |
| 94745998 | ETHINYL+DESOGES 20/150mcg tabs |
| 94773998 | ETHINYL+GESTODEN 30/75mcg tabs |
| 96439997 | Desogestrel with ethinylestradiol 150micrograms with 30micrograms tablets |
| 96439998 | Desogestrel with ethinylestradiol 150micrograms with 20micrograms tablets |
| 96922998 | ETHINYL+GESTODEN 30/75mcg tabs |
| 97670998 | Generic Tri-Minulet tablets |
| 97702998 | Generic Tri-Minulet tablets |
| 98178998 | ETHINYL+DESOGES 30/150mcg tabs |
| Drospirenone | |
| 53008979 | ETHINYLST+DROSPR 20mcg/3mg tab |
| 81032998 | Drospirenone with ethinylestradiol 3mg with 20micrograms tablets |
| 86831998 | DROSPIR 2mg/ESTRADIOL 1mg tabs |
| 86832998 | Estradiol 1mg / Drospirenone 2mg tablets |
| 92571998 | ETHINYLESTR+DROSPIR 30mcg/3mg |
| 98852998 | Ethinylestradiol 30microgram / Drospirenone 3mg tablets |
| Dienogest | |
| 82867998 | Generic Qlaira tablets |

| | |
|--------------------------------|--|
| 82869998 | estradiol valerate and (estradiol valerate with dienogest) tablets |
| New compounds | |
| 83740978 | NOMEGESTROL AND ETHINYLESTRADIOL |
| 83741978 | Estradiol 1.5mg / Nomegestrol 2.5mg tablets |
| 94996992 | ETHINYLLOESTRAD.50MCG/LYNOESTRENOL 2.5MG MCG TAB |
| 98176998 | Ethinylestradiol with lynoestrenol Tablet |
| Oral Progestogens | |
| 53167979 | Desogestrel 75microgram tablets |
| 53168979 | DESOGESTREL 75mcg tablets |
| 53169979 | DESOGESTREL 75mcg tablets |
| 53171979 | Desogestrel 75microgram tablets |
| 61400979 | DESOGESTREL 75mcg tablets |
| 82528978 | DESOGESTREL 75mcg tablets |
| 83545978 | DESOGESTREL 75mcg tablets |
| 85168978 | DESOGESTREL 75mcg tablets |
| 90580998 | DESOGESTREL 75mcg tablets |
| 90581998 | Desogestrel 75microgram tablets |
| 92598998 | NORETHISTERONE 1mg tablets |
| 93893998 | Norethisterone 350microgram tablets |
| 93986998 | Levonorgestrel 30microgram tablets |
| 95699998 | Norgestrel 75microgram tablets |
| 96765998 | Etinodiol 500microgram tablets |
| 97451998 | LEVONORGESTREL 37.5mcg tabs |
| 97452998 | LEVONORGESTREL 30mcg tablets |
| 97599998 | ETYNODIOL DIACET 500mcg tabs |
| 98170998 | LEVONORGESTREL 30mcg tablets |
| 98172998 | Norethisterone 350mcg tablet |
| 98174998 | Norethisterone 350mcg tablet |
| Ring | |
| 83186998 | Ethinylestradiol 2.7mg / Etonogestrel 11.7mg vaginal delivery system |
| 84617998 | Ethinylestradiol 2.7mg / Etonogestrel 11.7mg vaginal delivery system |
| Patches | |
| 89295998 | Norelgestromin with ethinylestradiol 203micrograms + 33.9micrograms/24hours Transdermal patch |
| 91878998 | Ethinylestradiol 33.9micrograms/24hours / Norelgestromin 203micrograms/24hours transdermal patches |
| 94918998 | ETHINYL+NOREL 600mcg/6mg patch |
| Injections Progestogens | |
| Gemsript codes | |
| 85241998 | MEDROXYPROGEST 150mg/1mL inj |
| 85242998 | Medroxyprogesterone 150mg/1ml suspension for injection pre-filled syringes |
| 94485998 | Medroxyprogesterone acetate 80mg/ml Oral suspension |
| 94789998 | Medroxyprogesterone acetate 80mg/ml Oral suspension |
| 95700998 | Norethisterone 200mg/1ml solution for injection ampoules |
| 97454998 | NORETHISTERONE 200mg/1mL inj |
| 97920998 | MEDROXYPROGEST 150mg/1mL inj |
| 97921998 | MEDROXYPROGEST 50mg/mL inj |
| Read Codes | |
| 61B..00 | Depot contraceptive |

| | |
|-----------------------------|---|
| 61B..11 | Depot contraception |
| 61B1.00 | Depot contraceptive given |
| 61B1.11 | Depo-provera injection given |
| 61B2.00 | Depot contraceptive repeated |
| 61B3.00 | Depot contraceptive-no problem |
| 61B4.00 | Depot contraceptive - problem |
| 61B5.00 | Depot contraception stopped |
| 61BZ.00 | Depot contraceptive NOS |
| Implant Progestogens | |
| Read Codes | |
| 61K..00 | Subcutaneous contraceptive |
| 61KA.00 | Insertion of subcutaneous contraceptive |
| 61KB.00 | Check of subcutaneous contraceptive |
| 61KD.00 | Subcutaneous contraceptive in situ |
| 61KE.00 | Subcut contraceptive implnt palp |
| 61KZ.00 | Subcutaneous contraceptive NOS |
| 7G2AB00 | Insertion of subcutaneous contraceptive |
| 7G2H700 | Removal of subcutaneous contraceptive |
| 9m7..00 | Contraceptive implant removal invitation |
| 7G2AA00 | Insertion of Norplant |
| 7G2H500 | Removal of Norplant |
| Gemscript | |
| 81886998 | ETONOGESTREL 68mg implant |
| 90908998 | Etonogestrel 68mg implant |
| 90909998 | ETONOGESTREL 68mg implant |
| 92888998 | LEVONORGESTREL 38mg implant |
| 98222998 | Levonorgestrel 228mg Implant |
| LNGIUSs | |
| Read | |
| 615S.00 | Mirena coil check |
| 7E09500 | Removal of Mirena coil |
| 7E09400 | Introduction of Mirena coil |
| Gemscript | |
| 91324998 | Levonorgestrel 20micrograms/24hours intrauterine device |
| 91325998 | LEVONORGESTREL 52mg i-u system |

Table 16.3 ATC codes to identify treatment for acne in the year before index date in PHARMO and HSD

| Substance | ATC code* |
|---|------------------------------------|
| Topicals | |
| Topical antibiotics | D10AF |
| Corticosteroids in topical combinations | D10AA |
| Topical retinoids | D10AD |
| Other topical preparations | D10AB, D10AE, D10AX, D01AE12 |
| Systemic preparations | |
| Systemic retinoids | D10BA |
| Systemic antibiotics | J01AA08, J01AA07, J01AA02, J01FA01 |
| Other systemic preparations | D10BX |
| Hormonal agents | |
| Hormonal contraceptives | G03A |
| Anti-androgens | G03H |

NOTE: preliminary table, final codes will be selected based on local guidelines as described in section 9.3.

Table 16.4 Gemscript codes to identify treatment for acne in the year before index date in THIN

| Gemscript | Descriptor |
|-------------------|---|
| Topical solutions | |
| 74977994 | Generic aknicare lotion |
| 74979994 | Generic aknicare cream |
| 74985994 | Generic aknicare sr skin roller |
| 81780998 | Benzoyl peroxide 10% wash |
| 81783998 | Benzoyl peroxide 10% aq.gel |
| 81814998 | Benzoyl peroxide 5% gel |
| 82355998 | Benzoyl peroxide 10% gel |
| 82356998 | Benzoyl peroxide 5% gel |
| 82430998 | Adap 0.1% / ben perox 2.5% gel |
| 82431998 | Adapalene 0.1% / benzoyl peroxide 2.5% gel |
| 82939978 | Benzoyl perox+clind 3%/1% gel |
| 82940978 | Benzoyl peroxide 3% / clindamycin 1% gel |
| 82985998 | Nicotinamide 4% topical gel |
| 85337998 | Clindamycin 1% gel |
| 85550998 | Salicylic acid & sulphur cream |
| 85606998 | Azelaic acid 15% gel |
| 85608998 | Azelaic acid 15% gel |
| 86859998 | Nicotinamide 4% topical gel |
| 87171998 | Tretinoin with hydrocortisone and hydroquinone 0.1% + 1% + 5% cream |
| 87527998 | Benzoyl peroxide 5% / clindamycin 1% gel |
| 87865998 | Benz perox 5% / clindam 1% gel |
| 87866998 | Clindamycin 1% with benzoyl peroxide 5% gel |
| 88057996 | Chlorhexidine gluconate 1% solution |
| 88087998 | Erythromycin 4% topical gel |
| 88090998 | Erythromycin 2% topical gel |
| 88921998 | Benzoyl peroxide 10% lotion |
| 88923998 | Benzoyl peroxide 5% lotion |
| 89203998 | Nicotinamide 4% topical gel |
| 89241997 | Adapalene 0.1% cream |
| 89241998 | Adapalene 0.1% topical gel |
| 89242997 | Adapalene 0.1% cream |
| 89242998 | Adapalene 0.1% gel |
| 89561998 | Benz perox+pot hydrox sulf cream |
